NCT Number: NCT03584633

Official Title: Standardization of Indocyanine Green Lymphography Protocol With Exercise for

Lymphedema Assessment

Document date: December 24, 2019

Exercise-Enhanced ICG Lymphography

TRIAL STATISTICIAN [name] Protocol Version (SAP associated with) TRIAL PRINCIPAL INVESTIGATOR: [name] SAP AUTHOR(s) [name], [name]

Abbreviations and definitions

Indocyanine Green ICG
SD Standard deviation
SPSS Statistical package for the social sciences

Background:

Indocyanine green (ICG) lymphography is a non-radioactive, fluorophore-based imaging modality that provides functional imaging of the lymphatic system. With specificity comparable to and sensitivity superior to technetium99-based lymphoscintigraphy, the conventional diagnostic gold standard, ICG lymphography has been increasingly relied upon to diagnose extremity lymphedema. The diagnosis of lymphedema is confirmed when the pathologic dermal backflow patterns are seen. In addition to providing a definitive diagnosis, the

types/distribution of the dermal backflow patterns presently allows the determination of disease

severity. Since the dermal backflow patterns emerge in a delayed fashion and, after their initial emergence, they continually evolve until reaching a steady-state, or plateau, a delayed scan at the time of plateau is necessary to achieve an accurate representation

of the disease. Exercise has been shown to accelerate lymphatic drainage.

Study Objectives:

To determine if controlled exercise could shorten the time it takes for ICG lymphography to reach a plateau, and to create a standardized protocol to increase the efficiency and reliability of

ICG lymphography to diagnose extremity lymphedema.

Study Methods:

Design: non-randomized controlled trial

Recruitment:

All lymphedema patients presented to our lymphedema reconstruction center over a 6-month. period and those who met inclusion criteria were recruited into the study.

Inclusion criteria: 18 years or older, having voluntarily agreed to participate in the study, and being suspected to have lymphedema or previously diagnosed with lymphedema. Exclusion criteria: allergy to iodine, women who were pregnant or nursing, having heart/lung/joint conditions that would prevent exercising.

Exercise protocol:

Patients presented for a one time visit. Following standard ICG injections, patients were

exercised on a recumbent cross-trainer at five-minute intervals at specific, controlled intensity. Delayed scanning was performed following each exercise interval, and sequential changes of lymphographic patterns were recorded. The cycle of exercise/scan continued until achieving a plateau, or when no further lymphographic changes were observed for two consecutive cycles. Following the point of the plateau, further delayed scanning was performed every hour to identify the time point when the lymphographic patterns started to recede. Twenty-three limbs in

9 patients (10 arms, 13 legs) with unilateral and bilateral lymphedema were studied. Campisi criteria were used to clinically stage disease severity.

Statistical analysis (SAP version: 2.0)

All patients who participated in the study were included in the analysis and the analysis compared the individuals' affected limbs to the unaffected limbs. Video footage of indocyanine green lymphography was independently reviewed by three experienced ICG lymphographers to identify time points of ICG plateau and regression.

SPSS was used to perform the data analysis using a significance level of 0.05 and a confidence interval of 95%. Descriptive analysis generated frequencies of the study variables, and comparisons of categorical variables were performed using the chi-square test.

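### The plan describes no time to plateau without exercise, so its data cannot show that exercise shortens that time

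*Combined protocol and SAP*

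**What the plan says.** Study Objectives gives two aims. The first is "To determine if controlled exercise could shorten the time it takes for ICG lymphography to reach a plateau"; the second is to create a standardized imaging protocol. Study Methods labels the study "Design: non-randomized controlled trial" without saying what the control is.

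The Exercise protocol section describes a single session: "Patients presented for a one time visit". After injection they were "exercised on a recumbent cross-trainer at five-minute intervals at specific, controlled intensity". On imaging it says "Delayed scanning was performed following each exercise interval", and on stopping, "The cycle of exercise/scan continued until achieving a plateau, or when no further lymphographic changes were observed for two consecutive cycles". Hourly scans then follow, but only after plateau, and they serve to time regression. The sample is 23 limbs in 9 patients, 10 arms and 13 legs.

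The Background says of the backflow patterns that "they continually evolve until reaching a steady-state, or plateau". It gives no numerical time to plateau at rest, and its remark that exercise speeds lymphatic drainage carries no figure.

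Statistical analysis (SAP version: 2.0) states one comparison: "the analysis compared the individuals' affected limbs to the unaffected limbs". The only test named is the chi-square test for categorical variables. No estimator is given for a difference in time to plateau.

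**The concern.** To say that exercise shortens a time, one must know or estimate what the time would have been without exercise. Nothing in the plan supplies that. By the Background's own account the patterns settle to a plateau in any case, so a plateau reached during the exercise cycles is what one would expect even if exercise did nothing.

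The design label makes this worse. A reader told that the trial was controlled may take a short time to plateau as evidence that exercise worked. If the plan is followed exactly, exercise could be credited with a plateau that would have come at the same time without it. One of the two stated aims would then be reported as answered when the data cannot answer it.

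**Working it through.** **Reproducing the plan's figure.** The only relevant figure is the limb count: 10 arms + 13 legs = 23 limbs, which agrees. No sample size, power, effect size or SD is stated, so there is no such calculation to reproduce.

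**Searching for a comparator.** Each possible source of an unexercised time was checked against the text.

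| Possible source | What the plan gives |
|---|---|
| Separate resting session | None; one visit per patient |
| Unexercised group | None described |
| Unexercised limbs | The plan does not say which limbs worked on the cross-trainer; it neither identifies nor compares any that did not |
| Sequence within the session | Delayed scans before plateau follow exercise intervals, so exercise and elapsed time rise together |
| Hourly scans | After plateau, too late to inform time to plateau |
| Published or historical resting time | None quantified |

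Unexercised times to plateau described: 0.

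**Can the limb contrast stand in?** Let A and U be the mean resting times to plateau in affected and unaffected limbs, and dA and dU the shortening by exercise in each, allowed to differ. Assume that all observed limbs count as exercised and that a plateau time is defined in both limb types. The observable means are

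- affected: A − dA
- unaffected: U − dU

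In the order (A, U, dA, dU) the design matrix has rows (1, 0, −1, 0) and (0, 1, 0, −1), hence rank 2 for 4 unknowns. Any weighted sum of the rows has the form (a, b, −a, −b). To isolate dA one needs (0, 0, 1, 0). The third entry forces a = −1, but then the first entry is −1 and not 0. So dA is not estimable, and by the same argument neither is dU. The planned contrast estimates (A − U) − (dA − dU), a difference by disease status under exercise.

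A single common exercise effect does not help. With an intercept, an affected-limb indicator and an exercise indicator equal to 1 for all 23 limbs, the rank is 2 for 3 parameters. The plan does not give the affected/unaffected split, so splits of 9, 10, 13 and 14 affected limbs were tried; the rank was 2 each time. If resting means existed for both limb types, the four-parameter model would have rank 4 and both effects would be estimable.

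**Illustration with assumed values (minutes; not from the plan).**

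| A | U | dA | dU | A − dA | U − dU | Contrast |
|---|---|---|---|---|---|---|
| 30 | 20 | 0 | 0 | 30 | 20 | 10 |
| 45 | 25 | 15 | 5 | 30 | 20 | 10 |
| 60 | 40 | 30 | 20 | 30 | 20 | 10 |
| 90 | 40 | 60 | 20 | 30 | 20 | 10 |

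Exercise effects in affected limbs of 0, 15, 30 and 60 minutes produce the same observed means.

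**What can be estimated.** The distribution of time to plateau under the protocol can be described. With one value per patient and n = 9, the distribution-free interval for the median from the 2nd to the 8th ordered value has coverage 1 − 2 × P(Bin(9, 0.5) ≤ 1) = 1 − 2 × (1 + 9)/512 = 1 − 20/512 = 0.961. Times recorded on a grid of cycles will probably be tied, in which case 96.1% is a lower bound on coverage.

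**The case against.** There are four serious counter-arguments.

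- **A comparator exists.** The SAP compares affected with unaffected limbs of the same individuals, so the study is not wholly without one. That is correct, and the point should be read as the absence of any control *for exercise*. Both kinds of limb belong to patients exercised in the same visit, and the plan nowhere calls the unaffected limb the control.
- **Silence is not exclusion.** The sponsor may hold an external resting time, or a fuller protocol may describe one. The text neither cites nor quantifies such a time. If one exists, its source and the estimator for the difference must be stated. It would then be an external comparison, and the study's own data would still not identify the effect.
- **Limb-level exposure is unclear.** Treating every limb as exercised is an assumption, and it is labelled as one above. If some limbs were idle, the plan still does not identify or compare them.
- **The numbers are illustrative.** The rank result puts the missing comparator in algebraic form, and the minute values are assumed. Whether unaffected limbs have a plateau time in the same sense is not established. The median interval also needs a rule for choosing one value per patient. All this is fair, but the defect rests on the missing resting time and not on these figures.

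The documents are in the past tense and report 9 patients as studied, so the design is settled. That argues for a wording remedy, not for leaving the claim as it is.

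**Conclusion.** The concern holds, with high confidence, and must be fixed. The effect of exercise on time to plateau is not identified, whether or not it is the same in both limb types, and a larger sample under the same design would not identify it. One of the two stated aims therefore cannot be answered by the planned data, and the design label claims a control for exercise that is not described.

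The conclusion assumes only that no unexercised time to plateau exists beyond what the documents describe. The standardized-protocol aim is untouched by this point, and the affected-versus-unaffected contrast remains estimable as a description of disease status.

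**What to change.** 1. Relabel the design as a single-group study. Keep the word controlled where it describes exercise intensity.
2. Keep the stated objective on record, and add that its shortening part cannot be tested with these data.
3. Limit the conclusion to estimates of time to plateau and time to regression under the exercise protocol. Report each with an interval at patient level, and state how one value per patient is obtained. A rule is needed because 23 limbs in 9 patients exceeds two per patient (2 × 9 = 18). Say also that hourly scans place regression only within about an hour.
4. State in the SAP that the affected-versus-unaffected contrast describes disease status and does not test exercise.
5. Keep the standardized-protocol aim.

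If the sponsor wishes to discuss shortening against an outside resting time, it should name the source and the estimator and present the result as an external comparison.

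The cost is wording in the design label, the SAP and the permitted conclusion, together with a weaker claim. No new patients or procedures are needed.

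### Does the unstated clock and dating point for time to plateau call for a change to the plan?

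*Combined protocol and SAP*

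**What the plan says.** The first aim in Study Objectives is "To determine if controlled exercise could shorten the time it takes for ICG lymphography to reach a plateau". Creating a standardized protocol is the second. No primary endpoint is named, so treating time to plateau as the main quantity is an inference, though a natural one.

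The Exercise protocol section has patients exercise in five-minute blocks after injection, with imaging after each: "Delayed scanning was performed following each exercise interval, and sequential changes of lymphographic patterns were recorded". The stopping criterion is: "The cycle of exercise/scan continued until achieving a plateau, or when no further lymphographic changes were observed for two consecutive cycles". After plateau, "further delayed scanning was performed every hour to identify the time point when the lymphographic patterns started to recede". The sample is given as 23 limbs in "9 patients (10 arms, 13 legs) with unilateral and bilateral lymphedema were studied".

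Under Statistical analysis, "the analysis compared the individuals' affected limbs to the unaffected limbs". The footage was "independently reviewed by three experienced ICG lymphographers to identify time points of ICG plateau and regression". The only test named is for categories: "comparisons of categorical variables were performed using the chi-square test".

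The plan therefore gives a criterion for plateau and names who dates it. It does not give time zero, the length of a scan, whether scan time counts, or which scan dates the plateau. It also does not say whether the two-cycle rule was applied live to each limb or to the patient as a whole.

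**The concern.** If the aim is a shorter time, the reader wants to know what time is being counted. Two clocks are natural: minutes of exercise, and minutes elapsed from injection. Two dating points are also natural. During the visit, plateau is known only at the second unchanged scan. On video afterwards, the last scan that showed change is just as obvious a choice. Three readers could agree on every image and still give times two cycles apart.

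The stake is the absolute time. A centre adopting a standardized protocol would use that number, and a time without exercise exists only on the elapsed scale, so setting exercise minutes against it would mix scales. There is a second worry about the unit. If a single plateau time were recorded per patient, the affected and unaffected limbs of one person would have a difference of zero by construction.

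**Working it through.** The plan gives no time to plateau, power or sample-size calculation to reproduce. The limb count is consistent: 10 + 13 = 23.

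**Inputs from the Exercise protocol section:** 5 minutes per exercise interval; one scan per interval; two unchanged cycles to confirm plateau.

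**Assumed, because the document is silent:** last change at cycle k = 6; scan length s = 1, 2 or 5 minutes; exercise starts at injection; each event is dated at the end of its scan.

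**Formulas.** Let d = 0 for dating at the last changed scan and d = 2 for the confirming scan.
- Exercise clock: 5(k + d)
- Elapsed clock: (5 + s)(k + d)

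**Absolute time for one limb, k = 6**

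| s (min) | Exercise, last change | Exercise, confirming | Elapsed, last change | Elapsed, confirming |
|---|---|---|---|---|
| 1 | 5×6 = 30 | 5×8 = 40 | 6×6 = 36 | 6×8 = 48 |
| 2 | 30 | 40 | 7×6 = 42 | 7×8 = 56 |
| 5 | 30 | 40 | 10×6 = 60 | 10×8 = 80 |

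The 2-minute row gives a range of 30 to 56 minutes. Even that depends on the end-of-scan convention: dated at the start of the scan, the elapsed values are 42 − 2 = 40 and 56 − 2 = 54.

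**The part that does not depend on k.** The dating gap is 2 × 5 = 10 exercise minutes, or 2(5 + s) = 12, 14 or 20 elapsed minutes. It is a fixed two cycles, so anyone who knows the convention can convert one date to the other.

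**Apparent shortening.** The document gives no time without exercise. Against a purely hypothetical 120 minutes:
- Exercise clock: 1 − 30/120 = 75%; 1 − 40/120 = 67%.
- Elapsed, s = 1: 1 − 36/120 = 70%; 1 − 48/120 = 60%.
- Elapsed, s = 2: 1 − 42/120 = 65%; 1 − 56/120 = 53%.
- Elapsed, s = 5: 1 − 60/120 = 50%; 1 − 80/120 = 33%.

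The full spread is therefore 75 − 60 = 15 points with 1-minute scans, 22 with 2-minute scans and 42 with 5-minute scans. It is about 8 points if scanning takes almost no time. These sizes come from the assumed scan length and baseline, not from the plan.

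**The comparison the plan does state.** For two limbs of one person with last changes at cycles k₁ and k₂, timed under one convention:

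(5 + s)(k₁ + d) − (5 + s)(k₂ + d) = (5 + s)(k₁ − k₂)

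The term d drops out. With k₁ = 6 and k₂ = 3, the exercise-clock difference is 30 − 15 = 15 or 40 − 25 = 15. With 2-minute scans the elapsed difference is 42 − 21 = 21 or 56 − 35 = 21. The clock rescales the difference by 1 + s/5 but cannot change its sign or the ordering of the two limbs.

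**The unit.** A per-patient time would give both limbs max(6, 3) = 6 cycles and a difference of 0. But the plan counts 23 limbs in 9 patients (23/9 = 2.6 each), splits them into arms and legs, and compares affected with unaffected limbs. A per-patient time would make that comparison empty, so per-limb timing is the reading that fits the text.

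**The case for a change.** The best argument for acting is that the second aim is a standardized protocol. The offset cancels between limbs but not in the absolute time, which is what others would adopt, and settling the convention would take only a few lines. That much stands: the convention is unstated, nothing elsewhere in the document supplies it, and a published time without it would be hard to use.

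The rest of the argument carries less weight. The 30-to-56-minute range and the shortening percentages rest on a scan length, a cycle of last change and a baseline that the document does not give. If plateau time were cut into categories for the chi-square test, the dating choice could move limbs across the cut. With a 30-minute cut and last changes spread evenly over 15 to 45 minutes, 4 of 7 grid points fall at or below it by last change and 2 of 7 by confirming scan. But nothing says the time is categorized, and the abbreviation list includes the standard deviation, which suggests a continuous summary was in view. Whether the live stopping rule ran per limb or per patient is open, yet each limb's own changes can still be read from its footage.

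Finally, the section is written in the past tense, with limbs already studied and footage already reviewed. New SAP lines would record what was done, or require completed readings to be converted. They would not pre-specify anything.

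**Conclusion.** The omission is real, but it does not call for a change to the plan. It is a gap in detail. Plateau has a criterion and assigned readers, each way of timing it is defensible, and none is shown to favour a particular answer. Used consistently, any one of them leaves the direction and ordering of the within-person limb comparison intact.

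The firm part of the size is a two-cycle difference in the absolute time: 10 exercise minutes, plus two scan durations on the elapsed clock. Anything larger depends on assumed inputs. The conclusion assumes that all three readers used one convention, that times were read per limb, and that the report states the clock and dating point. Each is what a sensible analyst would do with this text.

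### The only named test is the chi-square, yet nearly every table from 23 limbs or 9 patients is too sparse for it, so the 5% level is not guaranteed; name one exact, patient-respecting method per comparison

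*Combined protocol and SAP*

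**What the plan says.** The section headed Statistical analysis (SAP version: 2.0) contains the whole inferential plan. The software is given ("SPSS was used to perform the data analysis"), the error level is fixed ("using a significance level of 0.05"), the descriptive part is stated ("Descriptive analysis generated frequencies of the study variables"), and for inference "comparisons of categorical variables were performed using the chi-square test". The contrast of interest is within person: "the analysis compared the individuals' affected limbs to the unaffected limbs".

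The sample size is given under Exercise protocol: "Twenty-three limbs in" "9 patients (10 arms, 13 legs) with unilateral and bilateral lymphedema were studied". Neither section gives an exact test, a continuity correction, an expected-count rule, a list of the categorical variables, the number of affected and unaffected limbs, or a way to handle several limbs from one patient.

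**The concern.** The Pearson chi-square p-value comes from a large-sample distribution. The usual condition for relying on it is an expected count of at least 5 in each cell of a 2x2 table. With 23 limbs, let alone 9 patients, that condition is almost out of reach, so the p-value compared with 0.05 may come from a test whose true error rate is lower or higher than 5%. Tables near the cut-off can change verdict with the version of the test used, and the plan does not say which version counts. This question is separate from whether limbs are independent: it would remain if each limb came from a different person. Any repair must nevertheless deal with both.

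**Working it through.** The documents give no sample-size or power figure, so there is nothing to reproduce. The limb counts agree: 10 + 13 = 23.

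**Inputs.** From the documents: N = 23 limbs, 10 arms and 13 legs, 9 patients, level 0.05. Assumed: the expected-count threshold of 5 (a convention; 3 was also tried), all group splits other than 10 v 13, and all category probabilities.

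**Step 1: expected counts in 2x2 tables.** Smallest expected count = (smaller row total x smaller column total) / N.
- N = 23, margins 11/12 by 11/12: 11 x 11 / 23 = 5.26. This is the only one of 121 margin pairs that reaches 5.
- Arms v legs, best case: 10 x 11 / 23 = 4.78.
- N = 9, best case: 4 x 4 / 9 = 1.78. None of 16 margin pairs qualifies.
- With a threshold of 3 instead of 5: 19 of 121 pairs for N = 23, and 0 of 16 for N = 9.

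**Step 2: larger tables.** Under the looser rule that 80% of cells have an expected count of at least 5, a 2x3 table needs 5 of its 6 cells to qualify, hence N of at least 5 x 5 = 25. No table of 23 can pass.

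**Step 3: true level of the uncorrected 2x2 test, independent units.** For groups of n1 and n2 with a common proportion p, the level is the sum of Bin(a; n1, p) x Bin(b; n2, p) over all tables with chi-square above 3.841. The maximum over p from 0.005 to 0.995 is:

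| Split | Maximum level |
|---|---|
| 10 v 13 | 0.053 |
| 11 v 12 | 0.055 |
| 9 v 14 | 0.060 |
| 8 v 15 | 0.048 |
| 7 v 16 | 0.051 |
| 6 v 17 | 0.056 |
| 5 v 18 | 0.053 |
| 4 v 19 | 0.076 |
| 3 v 20 | 0.056 |
| 2 v 21 | 0.079 |
| 1 v 22 | 0.089 |
| 4 v 5 patients | 0.039 |
| 3 v 6 patients | 0.039 |
| 2 v 7 patients | 0.098 |
| 1 v 8 patients | 0.101 |

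These are maxima. For 10 v 13 the level is 0.006 at p = 0.05, 0.038 at p = 0.2 and 0.053 at p = 0.5.

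**Step 4: sparse multi-category tables.** Simulation with 200,000 draws, four categories at an assumed 85/5/5/5%: 0.8% (10 v 13), 10.6% (3 v 20), 0.1% (4 v 5) and 9.9% (2 v 7). With four equal categories the level on 23 limbs is about 4.5% for both 10 v 13 and 3 v 20, so the extremes come from the skewed distribution.

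**Step 5: does the choice of test change decisions?** Take 0/5 v 9/18.
- Chi-square = 23 x (0 x 9 - 5 x 9)^2 / (5 x 18 x 9 x 14) = 46575 / 11340 = 4.107, p = 0.043.
- Fisher's exact test gives p = 0.116.

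Across the 152 non-degenerate 10 v 13 tables, Pearson and Fisher disagree at 0.05 in 8. In all eight Pearson is the significant one, for example 1/10 v 7/13 (0.029 v 0.074).

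**Step 6: floor of the exact paired test.** Exact McNemar with k discordant pairs has smallest two-sided p = 2 x 0.5^k. For k = 5 this is 0.0625, and for k = 6 it is 0.031.

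**The case against.** The strongest reply is that failing a rule of thumb does not show that the level is wrong. That stands. For the one split the document gives, 10 v 13, the excess over 5% is at most 0.3 percentage points, and 4 v 5 or 3 v 6 patients give a conservative test. A reader might infer that the chi-square p-values simply do not hold 5%. The documents do not support this: clear inflation needs very uneven splits, and not even all of those (3 v 20 peaks at 0.056), or an assumed skewed multi-category variable. None of these is documented.

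The wording also does not exclude a continuity correction, and a corrected 2x2 test stays at or below 0.019 for 23 limbs and 0.009 for 9 patients. This is true, but it means that the choice of p-value is open, which is itself a reason to fix it.

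Exact methods can disagree among themselves. For 2/6 v 0/17 the chi-square gives 0.013, Fisher 0.059, Boschloo 0.052 and Barnard 0.020. So asking for an exact test without naming it would not settle the matter.

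Finally, the main objective is time to plateau, which is not categorical, and no primary categorical endpoint is named. This limits the consequence. Dependence between limbs may also be the larger threat to the level. In an illustrative simulation with assumed cluster sizes adding to 23 and within-patient correlation 0.3 to 0.9, the limb-level chi-square ran at about 0.12 to 0.27 when whole patients fell in one group, and at 0.024 or lower when groups split within patients. This argues for a repair that also respects the pairing. It does not argue for keeping the chi-square.

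**Conclusion.** The point holds in a limited form. The only named test relies on an approximation whose usual condition is met by one 2x2 margin pattern at 23 limbs and by none at 9 patients. The 5% level is therefore not guaranteed. For independent units the uncorrected 2x2 test is usually near or below nominal and reaches about 0.08 to 0.10 for splits such as 4 v 19, 2 v 21, 1 v 22, 2 v 7 or 1 v 8. Sparse multi-category tables can run from about 0.1% to 11% under the assumed 85/5/5/5% distribution.

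These sizes rest on the threshold of 5, on assumed splits and category probabilities, and on independence, which is used only to isolate this issue. They show what the plan allows; they do not show that any reported p-value is wrong. The change should be made because it is cheap and because the planned contrast has an unstated split.

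**What to change.** Replace the chi-square sentence with one pre-specified exact method per comparison, for example:

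*Affected and unaffected limbs are compared with an exact within-patient permutation test, or with exact McNemar where each patient contributes one affected and one unaffected limb. Comparisons between patients use the Fisher-Freeman-Halton exact test on one value per patient. The asymptotic chi-square is not used. Exact McNemar cannot reach two-sided p < 0.05 with fewer than 6 discordant pairs; in that case only the estimate and its interval are reported.*

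The SAP should also list the categorical variables, give the number of affected and unaffected limbs, and say how several limbs become one value per patient. Fisher's test applied to 23 limbs is not a sufficient substitute: it mends the reference distribution but still counts limbs from the same person as independent.

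The cost is a change of wording and a re-run of the categorical comparisons. The downside is that exact tests are discrete and somewhat conservative, so some p-values will become less favourable. With at most 9 patients, the paired test may be unable to reach 0.05 at all.
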